### **Premature termination**

Participants may drop out at any point in the study. We will terminate participants who are not able to conform to study expectations such as meeting regularly and undergoing the assessments. If they are unable to engage in study activities per protocol, study staff will have a discussion with the participant to explain requirements of the study and reasons for inability to complete study requirements. Information or clinical information will be offered to those who are terminated or decide to drop out.

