**to meet mental health service needs of participants with depression and link them to professional care as needed.**

## **Preliminary studies**

**1. Feasibility and acceptability of a peer support intervention for depression.** We developed a peer support intervention and evaluated the feasibility and acceptability of peer support for participants. We examined participant and peer experiences of the program. We found that engagement was high (90% percent of participants attended all 8 meetings with the peer). The majority was African American participants (74%) and 85% had decrease in PHQ-9 scores [Mean 7.1 (SD 7.1) p-value < 0.001]. Loneliness decreased (pre-study mean  $36.7 \pm 5.4$ ; post-study mean  $31.4 \pm 16.7$ , p-value 0.03) and coping skills increased (pre-study mean  $65.6 \pm 13.2$ , post-study mean  $69.9 \pm 10.4$ , p-value 0.006). Participants emphasized the importance of a trusting relationship, credibility of the peer and usefulness of professional supervision in the program. Participants described benefits such as hope, changes in attitude, behavior, and insight. The program also successfully connected participants to community and clinical resources during and after the study. We successfully contacted 85% of patients at 12 months and assessed depression with the PHQ-9 by telephone. Sixty-eight percent of patients had PHQ-9 scores that remained below baseline scores by 5 points or more. After completion of the feasibility study, we recruited 27 additional participants (total of 57 participants) seeking to obtain greater experience with a larger sample of peers and participants to refine the peer program. We tried telephone delivery of the program for two participants. Although peers found the telephone convenient, relationship building was more difficult, and two participants missed telephone calls more frequently but attended in-person meetings regularly. Given the importance of problems of loneliness among our study participants, we continued with in-person meetings and used telephone calls infrequently when peers were unable to meet in person due to weather. We concluded that use of supervised peer mentors is a promising model of depression care delivery for participants. We conducted an analysis using data from 57 participants in the pilot study to assess whether self-efficacy predicted change in depression. We found that improvement in self-efficacy was associated with a decline in depression.

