## 3. General Description of Study Design

We propose a two-step study: (1) a usability study to design and assess the user experience of Peers plus; and (2) a pilot study to assess the intervention feasibility and acceptability. In the usability study, we will test Peers plus in two iterations of five dyads (participants and peer mentors, see Table 1). The RA will use zoom to conduct the usability survey and semi-structured interview at 2 weeks and upon completion of the peer support meetings. Analytics (e.g. duration of the video chat, content of the texts) will provide data regarding the intervention components during a 4 week period.

We will use the knowledge gained from the usability study to

**Table 1.** Study flow for usability (Phase 1) and feasibility study (Phase 2). The studies are sequential. Recruitment and enrollment procedures are identical. Intervention duration and data collection procedures of the studies differ and are described in this table.

Aim 1. Usability study Recruitment and enrollment (two cohorts of 5 dyads) 

• RA receives referrals, conducts telephone screen

• Clinician conducts clinical assessment (zoom) and obtains verbal informed consent

• RA conducts baseline assessment (Redcap)

• RA conducts technology training as needed (e.g. access texting on zoom)

• Eligible participant is matched with a peer mentor who schedules a video chat

User experience assessment of Peers plus 

• PM conducts weekly 4 video chats and sends daily texts to the participant over 4 weeks.

• RA conducts usability survey and brief semi-structured interview at 2 weeks [midpoint] and at 4 weeks with the participant and the peer mentor.

Aim 2: Feasibility study (20 older adult participants) 

• Recruitment and enrollment procedures are identical to the usability study

Peers plus Intervention 

• PM conducts 8 weekly video chats and sends daily texts to the participant over 8 weeks.

Assessments 

• RA conducts baseline assessment, post-study assessment and semi-structured interview at 8 weeks with the participant. RA conducts semi-structured interview at 8 weeks with PMs.

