## **Data collection**

### Quantitative data

Listed in Table 3 is the timeline of study measures for the usability and feasibility studies. Data obtained from participants recruited for this protocol will include sociodemographic information (e.g., age, race, ethnicity, etc.), attitudes toward technology and technology use, self-reported clinical information (past history of depression services, current mental health service use), self-reported psychosocial measures (physical, social and emotional function, depression, self-efficacy, coping and loneliness) and social determinants of health. We will measure engagement defined in two ways: 1) as attendance of 80% of meetings as reported by peer mentors  and 2) score on the Working Alliance Inventory-SR.

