### **3. Statistical and Qualitative Analysis**

**Statistical analysis** We will screen data for quality and integrity. We will obtain descriptive statistics to characterize study participants. Percentage of session attended and engagement will be reported as percentages. Inferential analysis of depressive symptoms over time will be conducted using longitudinal linear regression taking into account clustering (via multi-level modeling) since peer mentors will meet with several patients. The quantitative data will identify measured factors that are related to engagement and depression reduction so that the mHealth components for peer delivery can be refined.

**Qualitative data analysis** All audio recordings will be professionally transcribed. The transcripts will be analyzed using thematic analysis which is a flexible and commonly used approach in qualitative analysis. The study team members will proceed through 4 phases: 1) immersion in the data by reading and re-reading the data, 2) generation of initial codes, 3) sorting of codes into themes, and 4) review and refinement of themes based on coded extracts and relevance to the entire dataset. The PI and members of the study team have conducted and published numerous qualitative studies and are experienced in qualitative methods. To ensure trustworthiness, the PI and trained study team members will code a subset of transcripts independently, compare their agreement on segments of coded data and resolve disagreements through in-depth discussion. The PI and study team members will meet on a weekly basis during the data analysis period to discuss in depth the rationale for coding and theme generation, and will resolve disagreements by negotiated agreement. Qualitative data analytic software, NVIVO11, (QSR Intl, Durham UK) will be used. The manual of the intervention will be revised based on review and analysis of the qualitative and quantitative data.

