**Statistical Analysis**

Baseline characteristics, working alliance scores, and clinical and social outcomes were summarized. The Shapiro-Wilk test was applied to check the normality of each outcome measure. Paired-sample t-tests and Wilcoxon signed-rank test were conducted to assess the differences in outcome measures between baseline and post-study, as well as baseline and three-month follow-up scores, to determine statistical significance. For all analyses, a significance level of  $\alpha = 0.05$  was used for two-sided tests unless otherwise specified.

To assess the change in the primary outcome, depressive symptoms over time within the intervention group, a multilevel linear regression model was employed. This model included fixed effects for time points (e.g., baseline, post-intervention, and follow-ups) and covariates such as baseline loneliness, self-efficacy, working alliance scores, and demographic variables that might influence the intervention effects. Random intercepts and slopes were included to account for the repeated measures within participants, allowing for individual variability in both baseline levels and the trajectories of depressive symptoms over time. Additionally, random effects were specified at the peer coach level to account for the nested structure of the data, where participants were grouped by peer coaches. These analyses and data visualizations were conducted using R Statistical Software (v4.2.1; R Core Team 2022).

PHQ\_9

Model	Timepoint	Estimate	Std. Error	95% CI	p-Value	Effect Size(standardized coefficients)	Marginal R^2
Model 1: Basic	Baseline vs Poststudy	-1.93	0.79	(-3.513, -0.344)	0.018	-0.36	0.049
	Baseline vs 3-mons follow-up	-2.88	0.83	(-4.557, -1.209)	0.001	-0.54	
Model 2: Adjusted for demographics #	Baseline vs Poststudy	-1.93	0.79	(-3.509, -0.348)	0.018	-0.36	0.159
	Baseline vs 3-mons follow-up	-2.81	0.83	(-4.488, -1.137)	0.001	-0.53	
Model 3: Full Model ##	Baseline vs Poststudy	-1.78	0.77	(-3.336, -0.230)	0.025	-0.33	0.276
	Baseline vs 3-mons follow-up	-2.42	0.81	(-4.057, -0.784)	0.005	-0.45	

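### The termination rule removes participants on the engagement outcome itself and provides no outcome assessment afterwards, so later PHQ-9 scores would tend to be missing for the least engaged

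*Protocol*

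**What the plan says.** The rule is in the protocol's Premature termination paragraph (section 6): "We will terminate participants who are not able to conform to study expectations such as meeting regularly and undergoing the assessments". Staff are to discuss the study requirements and the reasons for not meeting them, and to offer information to people who are terminated or drop out. The paragraph mentions no further assessment.

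Engagement is defined in two ways under Data collection, Quantitative data. The first is "as attendance of 80% of meetings as reported by peer mentors"; the second is a Working Alliance Inventory score. Table 1 fixes the number of meetings for Aim 2: "PM conducts 8 weekly video chats and sends daily texts to the participant over 8 weeks". The Aim 2 section schedules assessments at baseline, post-study and 3 months, with no separate provision for people whose participation has ended.

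On analysis, the protocol says "Percentage of session attended and engagement will be reported as percentages", without saying of whom, and also "The quantitative data will identify measured factors that are related to engagement and depression reduction". The SAP says "Paired-sample t-tests and Wilcoxon signed-rank test were conducted to assess the differences in outcome measures between baseline and post-study", with the same comparison at 3 months, and adds a multilevel model for PHQ-9. It states no analysis set, missing-data method or sensitivity analysis.

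**The concern.** Two grounds for termination matter here. Not meeting regularly is the low end of the attendance measure. Not being assessed determines whether PHQ-9 is observed at all. If ending participation also ends assessment, as the paragraph naturally reads, outcome data are lost selectively from the people who engage least.

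Aim 2 asks whether the intervention is feasible and acceptable. A later trial needs to know what share of everyone enrolled engages, and what happens to depressive symptoms in those who stop meeting. The second would be unknown for the people it concerns. The planned look at factors related to engagement and depression reduction would also lose its low-engagement end.

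**Working it through.** **1. The plan's own figure.** The SAP's Model 1 gives a PHQ-9 change from baseline to post-study of -1.93, SE 0.79, 95% CI (-3.513, -0.344), p = 0.018. Using estimate ± t × SE with about 52 degrees of freedom gives (-3.515, -0.345) and p = 0.018, which agrees within rounding of the SE.

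**2. What a terminated participant contributes.** In Aim 2 the first PHQ-9 after baseline is the post-study one at 8 weeks.
- Terminated during the 8 weeks, with no later assessment: baseline only. The paired tests need two scores, so the person is excluded. In the multilevel model the person informs the baseline level but has no observed change.
- Terminated after the post-study visit: the 3-month score alone is missing, and the model can use the rest.
- The model's handling of missing scores relies on loss being explained by observed data in the model. Attendance is not among the covariates the SAP names.

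**3. Possible size for PHQ-9 (illustration).** Assumptions: attendance is normal; the lowest share p is unobserved; attendance and improvement have correlation r; the model SE is treated as a paired-difference SE with n = 28 to 32.
- SD of change = 0.79 × √28 to 0.79 × √32 = 4.2 to 4.5.
- Overstatement of mean improvement = r × λ × SD, with λ = φ(z_p)/(1 − p) = 0.109, 0.195, 0.274, 0.350 for p = 5, 10, 15, 20%.
- r = 0: none. r = 0.2: 0.09 to 0.31 points. r = 0.4: 0.18 to 0.63 points.

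The largest value is below one SE (0.79).

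**4. Effect on the engagement analysis (same assumptions).** Cutting off the low end reduces the variance of attendance to v = 1 + z_p λ − λ², which is 0.81 at p = 5% and 0.58 at p = 20%. A true correlation of 0.40 would appear as 0.40√v / √(1 − 0.16 + 0.16v) = 0.37 to 0.32.

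**5. How much the engagement denominator matters.** If k of N are terminated and not engaged, the all-enrolled rate is the retained rate × (N − k)/N. Take an assumed 90% among retained and k = 1 to 4:
- N = 20 (protocol): 85.5, 81.0, 76.5, 72.0%.
- N = 32 (SAP's approximate figure, taken as enrolled): 87.2, 84.4, 81.6, 78.8%.

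Reading the bar as at least 80%, 0.8 × 8 = 6.4, so 7 of the 8 meetings are needed. The meeting denominator matters too: someone who attended 3 of 4 and was then terminated has 75% of meetings to date but 3/8 = 37.5% of those scheduled. The protocol gives no attendance cut-off for termination, so this example is hypothetical.

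**6. What the proposed sensitivity table would look like.** Assume 28 observed and 4 unassessed. The mean over all 32 is (28 × -1.93 + 4d)/32, where d is the change assigned to the unassessed: -1.69, -1.56, -1.44, -1.31 for d = 0, +1, +2, +3. These are means only; no tipping point is claimed.

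**The case against.** The strongest reply is that the harm rests on things the plan does not say. The rule never states that the post-study and 3-month visits are cancelled, and the schedule makes no exception. That is fair as far as it goes, but nothing says assessments continue, and one stated ground for termination is failure to be assessed. One sentence would settle it.

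A reader might infer that the reported engagement rate will be inflated. The documents do not support this. No retained-only denominator is stated, and the Recruitment paragraph tracks numbers enrolled as well as retained. The gap is an unspecified denominator, not a biased one.

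A reader might also infer that the SAP's PHQ-9 results are shown to be biased by terminations. The midpoint of the post-study interval, -1.9285, equals -54/28. With whole-number scores and the same people at both visits, that fits 28 pairs, set against an approximate 32 in the SAP. This is an inference about n. It does not show that anyone was terminated, and the figure of 32 may not be the enrolled count.

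Nor is mentor-reported attendance shown to be unreliable. The supervising mental health professional keeps meeting logs and reviews recordings, so the data source is a separate matter and no change to it is proposed.

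Three further points stand as limits. Weekly alliance scores and call counts exist up to termination, so it is mainly the later PHQ-9 that is lost. The SAP is written in the past tense and already reports post-study and 3-month results, so continued assessment may come too late for some or all visits. This is a preliminary single-arm pilot with no stated progression threshold that a shift could cross.

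**Conclusion.** The concern holds as a design weakness. The rule selects on attendance and on being assessed, provides no outcome assessment afterwards, and feeds analyses that cannot recover change in people with a baseline score only. PHQ-9 would tend to be missing for the least engaged.

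The number lost is not given. Under the stated assumptions the overstatement of improvement runs from 0 to about 0.6 points; the direction is plausible but not proven, and with no correlation between attendance and improvement there is none. The engagement denominator is a point to clarify, worth 1/N of the retained rate for each terminated non-engager: 4.5 percentage points at a 90% rate with N = 20 (0.90/20). The correction is cheap and bears directly on the feasibility aim.

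**What to change.** (a) Amend Premature termination to say that ending peer meetings does not end outcome assessment. All enrolled participants who have not withdrawn consent are invited to the 8-week and 3-month assessments, by telephone if needed. The protocol already allows telephone data collection, and the team reports of its earlier pilot: "We successfully contacted 85% of patients at 12 months and assessed depression with the PHQ-9 by telephone". Where these visits have passed, report n per visit and reasons for loss against the number enrolled.

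(b) State that engagement is reported over all enrolled participants and all 8 scheduled meetings. Terminated participants count as not engaged unless they had already met the 80% bar.

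(c) Add one sensitivity table to the SAP that sets the PHQ-9 change of unassessed participants to 0, +1, +2 and +3 points. These are assigned values, not shifts from the observed mean.

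The cost is protocol and SAP wording, one table from existing data, and $30 per extra assessment under Remuneration; four people at two visits would be 4 × 2 × $30 = $240. Some people terminated for declining assessments will decline again, and the engagement and PHQ-9 figures may look less favourable. No view is taken on when peer meetings should stop.

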### **Remuneration**

**Usability study:** Participants will receive \$30 for each assessment(4) and meeting(4) with the peer mentor. Assessments will include baseline, 2 weeks, post-study assessment and semi-structured interview for a total \$240. **Peer mentors** will receive \$50 for each meeting and supervision (4) and \$20 post study semi-structured interview. Total provided for completing all study activities will be \$220.

**Feasibility study:** **Participants** will receive \$30 for each assessment and interview (4). Assessments will include baseline, post-study assessment, 3 month follow-up and semi-structured interview for a total \$120. **Peer mentors** will receive \$50 for each meeting with the participant and supervision (8) and \$20 post study semi-structured interview. Total payment provided for completing activities with one participant will be \$420.

## 1. Risks and Discomforts

### Psychosocial risks

We recognize that older individuals, especially those with chronic illness, can easily feel overwhelmed or fatigued by what would be minimally demanding tasks for others, and, therefore, we include this discomfort in the potential risks. A minority of participants may respond to certain interview questions with feelings of sadness and grief (e.g., upon being reminded of interpersonal problems and social isolation). To address undue emotional stress, multiple strategies were used to prevent adverse events: 1) rigorous screening of the older adult's appropriateness for a peer mentor intervention, performed by a mental health professional prior to matching, 2) rigorous training and continuous supervision of the peer to prevent escalating emotional distress, and 3) availability of professional staff to address peer mentor's concerns by phone at all times. In the event that the peer mentor needs assistance, the peer will contact the supervising MHP (with geriatric psychiatrist backup) who will speak with the participant regarding the problem. In our experience, peers have been able to detect signs in the participant of escalating distress and able to follow the established protocol without adverse events. Peer mentors will be trained to recognize and provide support to manage undue emotional distress. In the case that a participant is distressed, the peer mentor will listen actively, provide empathy and ask if they would like to speak with a mental health professional on the study team. If the participant answers in the affirmative, the PM will inform the MHP and the MHP will call the participant and conduct a clinical assessment with appropriate triage to connect with community or clinical resources. If the participant declines speaking with the MHP, the PM will inform the MHP during weekly supervision and also follow up with the participant at the next meeting. The MHP will be available by telephone during the week 9-5pm and a geriatric psychiatrist will be available in the case that the MHP is unable to manage the participant's distress.

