## 6. STUDY PROCEDURES

Upon enrollment of the older adult participant, the RA will arrange delivery of devices by courier to those who do not have personal devices and provide any technology training that is needed to participants and PMs. Those participants will be given a WIFI enabled device to be returned when the study is completed. **Baseline assessment.** The RA will schedule and conduct the baseline assessment that lasts about 1 hour by zoom. The assessment will consist of questions regarding demographic information, medication use, depression care history, technology, and questionnaires to measure depression and function. Data will be entered directly into REDCAP MGH. All study documents will be in electronic form and stored on MGH OneDrive. **Matching and scheduling of visits.** After delivery and training in technology and the baseline assessment have been conducted, the PM will contact the participant to schedule weekly video chats. The weekly video chats will last for 45 – 60 minutes. Each video chat will be recorded. The peer mentor will be supervised by a mental health professional who will also review the audio recordings for quality assurance, on a weekly basis.

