**Component 2:** Supportive texting. In each dyad, the participant will receive one-way tailored text SMS messages delivered by the peer mentor daily during the 4 weeks of video chats. Supportive texts will be developed and conceptualized as “micro-interventions” informed by Motivational Interviewing that uses affirmations to motivate behavior change, e.g. use self-care skills for depression. To ensure that the texts are helpful, the peer mentor and the participant will discuss relevant self-care strategies during the video chats first. Based on discussion during the video chats, the peer mentors will send motivational and educational texts that are personalized, consisting of relevant affirmations (e.g. “you are taking great care of your loved one”), coping skills and community-based resources (e.g. “take time out for yourself”, “do something you enjoy”, “connect with a mental health professional”) daily to participants. Texts will serve to reinforce the trusting relationship, express empathy, encouragement, and self-care skills discussed during the video chats. The idea is that such texts encourage and support use of self-care behaviors that are related to depressive symptoms identified by the participant. The

texts will be declarative and posed as questions so that the effect is not to direct behavior but to stimulate thinking in the participant who then decides. All text messages will be co-developed by the mental health professional and the peer mentor before it is sent. The PM will keep a log of texts specifying the day and time when it was sent and will review this process with the MHP during supervision meetings.

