**Supervisory role of the mental health professional such as a social worker or a clinical psychologist (MHP).** Supervision is important to sustain the quality of the program and to support peer mentors. Peer mentors will meet in groups of 2 on a weekly basis concurrent with meetings with participants for supervision. During meetings, the MHP will elicit insights from PMs, discuss progress and problem-solve challenges e.g., lack of engagement and motivation. The MHP will document the activities of supervisory meetings, maintain logs of peer meetings with participants and review audio-recordings of meetings. The PI, who is a geriatric

psychiatrist, will be available for consultation to the MHP to problem-solve difficult situations as appropriate. PMs will have access to the MHP by telephone as needed outside of supervision meetings.

**Standard of Care/Referral to clinical care.** The participant will be asked if they want referral to specialty mental health care if not engaged in professional care at initial clinical evaluation, during the meetings with the peer mentor and upon completion of the study. If at any time the participant asks for referral to professional care, the participant will receive information about specialty mental health care services so they can make an appointment.

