### Suicidal ideation

When conducting studies with depressed patients, expression of suicidal ideation is a risk. We will address this risk in multiple ways. We will conduct a clinical evaluation prior to matching to assess the participant's appropriateness for the study in terms of depression severity and risk for suicidal ideation. In our previous work, expressions of suicidal ideation were rare because we assessed for depression severity and appropriateness for peer services during the initial clinical evaluation and such persons were excluded and referred for appropriate care. Also, peer mentors recruited for this study will receive training in a protocol for those participants who express suicidal ideation, to ensure the safety of the participants. If the participant

expresses suicidal ideation during a meeting, the peer mentor will immediately call the MHP who will call the participant and manage the situation. Assessment by the MHP may involve the following questions: (1) Do you have a desire to hurt yourself that you think you might act on? (2) Do you have a plan for hurting yourself and intend to carry the plan out? Participants may also be identified as a high risk for suicide if the participant reports a specific plan to commit suicide, or if the participant has risk factors for suicide. Risk factors may include multiple suicide attempts, moderate to severe depression, a high level of hopelessness, immediate access to a lethal method, a lack of reasons for living, psychosis or mania, poor social support or a recent stressful life event. Additional probing may be necessary to identify any other risk factors (e.g., access to a firearm). The MHP will ensure and facilitate urgent referral of high risk patients to the Emergency Department near their home where an evaluation to assess need for treatment is done. A geriatric psychiatrist ([name]) will be available for consultation in situations where the social worker needs assistance. In our experience, one instance of suicidal ideation (1 participant) did arise, the trained peer mentor contacted the PI who spoke with the participant and managed the situation without adverse events.

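### When a distressed participant without expressed suicidal ideation declines the clinician, no report is required before weekly supervision unless the peer mentor judges that help is needed

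*Protocol*

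**What the plan says.** The procedure for a distressed participant is in the Protocol, Risks and Discomforts, under Psychosocial risks. The mentor listens, shows empathy and offers a conversation with the MHP. If the participant accepts, the mentor tells the MHP, who calls and carries out a clinical assessment. If not: "If the participant declines speaking with the MHP, the PM will inform the MHP during weekly supervision". The mentor also raises the matter with the participant when they next meet.

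Other text bears on how soon the MHP could learn of a refusal:

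- Same section, a duty that depends on the mentor's need: "In the event that the peer mentor needs assistance, the peer will contact the supervising MHP (with geriatric psychiatrist backup". The MHP then speaks with the participant.
- Same section, availability: professional staff are to be on hand for a mentor's "concerns by phone at all times". Later in the section, the MHP's telephone hours are given as 9 to 5 on weekdays.
- Suicidal ideation: if it is expressed in a meeting, "the peer mentor will immediately call the MHP who will call the participant and manage the situation".
- Supervisory role of the MHP: "Peer mentors will meet in groups of 2 on a weekly basis concurrent with meetings with participants for supervision". Between sessions, "PMs will have access to the MHP by telephone as needed outside of supervision meetings".
- Study Procedures: the mentor is supervised by an MHP "who will also review the audio recordings for quality assurance, on a weekly basis".
- Component 2, Supportive texting: "All text messages will be co-developed by the mental health professional and the peer mentor before it is sent".
- Monitoring and Quality Assurance: the MHP reviews the mentor's activities for each meeting, in the weekly supervision sessions.

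**The concern.** The two branches differ in speed in a way that is hard to justify clinically. A distressed participant who accepts help gets an MHP call, with no wait for supervision stated. For one who refuses, the only clinician linked to the dyad need not hear of it until the next supervision. A refusal tells the mentor little about severity.

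The population makes this worth tidying. Participants enter with a PHQ-9 of 10 or more. The Protocol's own list of suicide risk factors goes beyond stated ideation to include moderate to severe depression, hopelessness, weak social support and recent stressful events. Weighing these is the MHP's job, and the MHP cannot do it for a case not yet reported. What is at stake is the timing of a clinical judgement in one branch of the safety procedure. No estimate, test or sample size is affected.

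**Working it through.** The Protocol states no reporting time in hours or days for this branch, so there is no figure to reproduce. The check has three steps.

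**Step 1. Does any other text require earlier notice?**

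- *Immediate call:* mandatory, but triggered only by expressed suicidal ideation.
- *Mentor needs assistance:* mandatory, but triggered only when the mentor judges that help is needed.
- *Telephone access between supervision sessions, and availability of professional staff:* these permit a call and do not oblige one.
- *Review of recordings:* weekly, so it guarantees no shorter interval.
- *Joint drafting of the daily texts:* brings mentor and MHP into contact, but no time is fixed and no report of distress is asked for.
- *Review of each meeting under Monitoring and Quality Assurance:* placed in weekly supervision, so the same interval applies.
- *Remuneration:* mentors are paid per meeting and supervision (8 in the feasibility study). This suggests one supervision per meeting, but does not fix the time between the two.

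Nothing in either document sets an earlier required report once the first two triggers are absent.

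**Step 2. Required wait under the current text.** The input is a supervision interval T = 7 days, read from the weekly schedule. The wait L from refusal to the next supervision satisfies 0 ≤ L ≤ T, so the ceiling is 7 × 24 = 168 h. If supervision is held a fixed d days after the chat, L = 24 × d hours:

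- d = 1: 24 h
- d = 3: 72 h
- d = 6: 144 h

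The Protocol does not give d. A missed supervision would push the wait past 7 days.

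**Step 3. Required wait after the proposed change.** Normally it is the same day. The longest ordinary case uses the weekday 9-to-5 hours: a refusal at 5pm on Friday with nobody reachable until 9am on Monday. That is 7 h (rest of Friday) + 24 h + 24 h + 9 h (Monday morning) = 64 h. The ceiling falls from about 168 h to about 64 h, a difference of 104 h. If supervision already follows one day after the chat, the present wait is 24 h and the gain is small.

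**The case against.** The best defence is that this is graded escalation by design. Expressed ideation brings an immediate call, a mentor in need of help contacts the MHP, and an accepting participant is called. What remains is the case with no ideation, a participant who does not want the MHP, and a mentor who sees no need for help. Distress has no severity threshold in the text, and the section has ordinary sadness or grief in view. A call after every refusal could seem heavy-handed where the Background notes distrust of medical professionals. A severity trigger would be an alternative. The section also refers to an established protocol and to mentor training, and an earlier reporting rule may sit there.

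Part of this stands. The branch is a narrow one, the unseen materials may already cover it, and the actual wait may be short. But the tiers leave the grading to a lay mentor, and a severity trigger would do the same. Participant choice is untouched, because the Protocol already requires that the MHP be told; only the timing would move.

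A reader might infer more than the documents support:

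- *That the safety plan fails.* It does not. Clinical screening before matching, the duty to seek assistance and the immediate call for ideation all remain.
- *That an average delay or a number of affected meetings can be given.* Neither can. The timing of chats relative to supervision is not stated, and there is no rate of distress with refusal.
- *That a refusal at the last meeting goes unreported.* Nothing exempts that meeting from supervision, and both the payment schedule and the review of each meeting suggest it is covered. Only the mentor's own follow-up at a next meeting lapses.

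**Conclusion.** The point holds as a cheap safety improvement to one branch. Where a distressed participant has not expressed suicidal ideation and declines the MHP, and the mentor does not judge that assistance is needed, required notice to the MHP is 0 to about 7 days.

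This rests on three things: the reading of weekly as a 7-day interval, supervision held on schedule, and the Protocol text alone without the manual or training materials. The 7 days is a ceiling on required notice and not an expected delay. Confidence is medium, mainly because of the unseen materials.

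**What to change.** Under Psychosocial risks, replace the clause on a participant who declines with wording such as:

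> the PM will inform the MHP by telephone the same day (or, if the MHP cannot be reached, at the start of the next working day), bring the case to weekly supervision, and raise it with the participant when they next meet; the MHP will decide whether further action is needed.

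Leave unchanged the duty to contact the MHP when the mentor needs assistance and the immediate call for suicidal ideation. If the manual or training materials already require earlier notice, bring the Protocol into line with them. The SAP reports results in the past tense; if enrolment is complete, the clause belongs in the manual revision that the Statistical and Qualitative Analysis section promises.

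The cost is one short call and one MHP decision per refusal. The documents do not say how often that would occur, so the added MHP time cannot be stated, though the telephone line already exists. Sample size and analysis are unaffected.
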